- Missing month/day, year present: If the year is the same as the year of the first IMP administration date, then impute missing start dates with first IMP administration date. Otherwise, for dates corresponding to a start date, impute with the first day of the year and, for dates corresponding to a stop date, impute with the last day of the year.
- Missing month/day/year: no imputation.
- In case imputed start date is after available stop date, the imputed start date will be replaced with the stop date to avoid negative durations.

This imputation method will be applied to the following dates:

- Onset date of AEs (for treatment-emergent purpose), incomplete AE end dates
- Medical history start date to define prior medical history and concomitant diseases
- Date of prior/concomitant medication (start dates) to define prior and concomitant medication, incomplete stop dates of prior/concomitant medications

Conventions for imputing missing/partial start dates of the subsequent anti-cancer therapy:

- If the start date of the first subsequent anti-cancer therapy is missing, it will be imputed with the date of the End of Treatment (EoT) visit.
- Missing day, month/year present: If the month/year is the same as the month/year of the EoT visit date, then impute missing start dates with EoT visit date. Otherwise, for dates corresponding to a start date, impute with the first day of the month and, for dates corresponding to a stop date, impute with the last day of the month.
- Missing month/day, year present: If the year is the same as the year of the EoT visit date, then impute missing start dates with the EoT visit date. Otherwise, for dates corresponding to a start date, impute with the first day of the year and, for dates corresponding to a stop date, impute with the last day of the year.
- If the EoT visit date is missing, the date of the last study treatment administration + 14 days to be used for the imputation.
- In case imputed start date is after available stop date, the imputed start date will be replaced with the stop date to avoid negative durations.

Clinical progression:

Clinical progression reported more than 14 days after start of the first subsequent anti-cancer therapy will not be considered in the analysis of clinical progression.

Best Overall Response (BOR) based on Radiological Soft Tissue Evaluation:

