8.7.4.1 Exploratory efficacy endpoints

Objective Response Rate based on iRECIST (central reading)

ORR based on iRECIST will be analyzed for mCRPC patients in Part 1 and Part 2 only.

The ORR is defined as the number of patients with iCR or iPR as best objective response per iRECIST divided by the number of patients in the mITT set. Patients not meeting the criteria for iCR or iPR, including those without any post-baseline tumor assessments, will be considered as non-responders. The ORR will be summarized with absolute and relative frequencies along with two-sided 95% Clopper-Pearson CIs by treatment group.

BOR (all categories) will be summarized with absolute and relative frequencies.

Tumor response assessment including overall response and BOR will be listed. In addition, listings including all tumor assessments per iRECIST (central reading) (target lesion, non-target lesion, new lesion) will be generated.

Duration of Response

DoR will be analyzed for Part 1 and Part 2 Arms 1A and 1B only. DoR will be analyzed separately for PCWG3 and iRECIST (central reading).

The DoR is defined as the time from the date of first radiographic documented OR to the date of first disease progression or death from any cause, whichever occurs first. Only patients who experience a confirmed OR will be analyzed for DoR.

In case death date is reported after trial discontinuation date, these death details will not be considered in the DoR analysis. The patient will be censored at the day of the last response assessment.

DoR will be analyzed using the Kaplan-Meier method. Kaplan-Meier plots will be generated.

Patients alive and without disease progression at data cut-off date or patients lost to follow-up will be censored at the day of their last response assessment.

Only response assessments prior to or at the start date of the first subsequent anti-cancer therapy will be considered for DoR analysis. PD within 14 days after the start date of the first subsequent anti-cancer therapy will be considered.

DoR based on PCWG3:

OR is defined as CR or PR. Disease progression is defined as tumor response = Progressive Disease (PD)

DoR expressed in months for patients whose objective response was confirmed CR or PR
= (MIN [Date of first documented disease progression (PD), date of death from any cause]
– Date of first documented overall response (CR or PR) + 1) / 30.4375 for events

or

(Date of the last evaluable response assessment – Date of first documented overall

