response (CR or PR) + 1) / 30.4375 in case of censoring.

DoR based on iRECIST (central reading):

OR is defined as iCR or iPR. Disease progression is defined as tumor response =
Confirmed progressive disease (iCPD)

DoR expressed in months for patients whose objective response was confirmed iCR or
iPR = (MIN [Date of first documented disease progression (iCPD), date of death from any
cause] – Date of first documented overall response (iCR or iPR) + 1) / 30.4375 for events

or

(Date of the last evaluable response assessment – Date of first documented overall
response (iCR or iPR) + 1) / 30.4375 in case of censoring.

Progression-free survival

PFS will be analyzed for Part 1 and Part 2 Arms 1A and 1B, Arm 2 and Arm 3.

PFS is defined as the time from the date of the first dose of IMP to the date of the first
disease progression, or death from any cause, whichever occurs first.

Only death dates reported prior to or at the date of trial discontinuation will be considered
in the PFS analysis.

PFS will be analyzed using the Kaplan-Meier method. Kaplan-Meier plots will be
generated.

Patients alive and without disease progression at the data cut-off date or patients lost to
follow-up will be censored at the day of their last response assessment.

Only response assessments prior to or at the start date of the first subsequent anti-cancer
therapy will be considered for PFS analysis. PD within 14 days after the start date of the
first subsequent anti-cancer therapy will be considered.

If no post-baseline tumor response is available, the patient will be censored at the date of
the first dose of IMP.

PFS expressed in months = (MIN [Date of first disease progression, date of death from
any cause] – date of first dose of IMP + 1) / 30.4375 if the patient has a PFS event

or

(Date of last evaluable response assessment – date of first dose of IMP + 1) / 30.4375 in
case of censoring.

In the case that date of the first dose of IMP is missing, randomization date will be used for the calculation of PFS.

For Part 1 and Part 2 Arms 1A and 1B, PFS will be analyzed separately based on PCWG3 and iRECIST (central reading).

Sensitivity analyses of PFS will be performed using the ITT set and the PP set depending on the number of patients excluded.

Overall survival

OS will be analyzed for Part 1 and Part 2 Arms 1A and 1B, Arm 2 and Arm 3.

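### PFS, DoR and PFS2 stop counting progression at the start of new anti-cancer therapy but keep counting deaths, so the rule neither censors at new therapy nor ignores it

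*SAP*

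**What the plan says.** SAP 8.7.4.1 builds PFS and DoR from four rules.

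- **Assessments.** For PFS, the rule opens "Only response assessments prior to or at the start date of the first subsequent anti-cancer". The one relaxation opens "PD within 14 days after the start date of the" and refers to the same new therapy. DoR has the same cut: "Only response assessments prior to or at the start date of the first subsequent anti-cancer therapy will be considered for DoR analysis". SAP 8.2 applies a matching limit to clinical progression, in the sentence that starts "Clinical progression reported more than 14 days after start of the first subsequent anti".
- **Deaths.** For PFS: "Only death dates reported prior to or at the date of trial discontinuation will be considered". For DoR: "In case death date is reported after trial discontinuation date, these death details will not be considered in the DoR analysis". Neither sentence mentions new therapy.
- **Event date.** The formula takes the earlier of progression and death: "PFS expressed in months = (MIN [Date of first disease progression, date of death from" any cause.
- **Censoring.** The rule covers "Patients alive and without disease progression at the data cut-off date or patients lost to" follow-up. A patient known to have died in the trial is in neither group.

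SAP 8.7.4.2 has the same structure for DoR, PFS and PFS2 in Arm 1B patients who switch to cemiplimab. SAP 8.1 says censoring follows a cited FDA guidance without reproducing its rules. Protocol 9.4.4 leaves additional censoring rules to the SAP.

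**The concern.** New anti-cancer therapy started before progression can be handled consistently in two ways. One is to end observation for the endpoint at that point, for progression and death alike. The other is to disregard the new therapy and count both whenever they occur. The SAP takes the first course for progression and the second for death.

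Two patients with identical records up to the start of new therapy are then treated differently according to whether they later die. One contributes follow-up to his last eligible assessment. The other contributes all of his time on the new treatment as event-free, although progression in that interval is not allowed to count and, in the mCRPC arms, imaging is no longer scheduled (Protocol 8.1.1.1).

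At stake is what the PFS, DoR and PFS2 curves mean, and what the exploratory log-rank tests and Cox hazard ratios in SAP 8.1 (Arm 1A versus 1B, Arm 2 versus 3) compare if use of new therapy differs between arms.

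**Working it through.** The plan states no figure for this point, so there is none to reproduce. The check applies the SAP rules literally to an invented patient.

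**Inputs from the SAP:** one month is 30.4375 days (8.2); assessments count up to the start of new therapy, plus PD within 14 days after it; the event is the earlier of counted PD and death; a death counts only if on or before trial discontinuation (8.7.4.1).

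**Assumed study days (not trial data):** SD on days 57 and 113, new therapy on day 120, PD on day 169, death on day 330. The PD is 169 − 120 = 49 days after new therapy, so it is not counted.

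**Formula:** PFS in months = study day of the event or of the last eligible assessment / 30.4375. DoR counts from day 57, assuming that assessment was instead a confirmed response.

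| Record | SAP as written | Both components stop at new therapy | Both counted regardless |
|---|---|---|---|
| PFS, dies day 330 in trial | 330/30.4375 = 10.84, event | 113/30.4375 = 3.71, censored | 169/30.4375 = 5.55, event |
| PFS, alive | 3.71, censored | 3.71, censored | 5.55, event |
| PFS, dies day 330 after leaving the trial on day 300 | 3.71, censored | 3.71, censored | 5.55, event |
| DoR, dies day 330 in trial | (330 − 57 + 1)/30.4375 = 9.00, event | (113 − 57 + 1)/30.4375 = 1.87, censored | (169 − 57 + 1)/30.4375 = 3.71, event |

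Each consistent rule gives one PFS answer for this patient whatever happens to him later. The SAP rule gives two, depending on whether a death is recorded before trial discontinuation. If the PD came on day 130, inside the 14 days, it would count: 130/30.4375 = 4.27 months, event. The inconsistency therefore needs no counted PD by 14 days after new therapy starts, together with a death in the trial.

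**Direction.** Put this patient (death at 10.84 months) with three others and compare the SAP rule with stopping both components at new therapy.

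- Others progress at 12, 14 and 16 months. At 11 months the SAP rule gives 3/4 = 75%. With the patient censored at 3.71 months the estimate is 100%. The SAP rule is lower.
- Others progress at 2, 4 and 6 months. At 9 months the SAP rule gives 3/4 × 2/3 × 1/2 = 25%. With censoring at 3.71 months it is 3/4 × 1/2 × 0 = 0%. The SAP rule is higher.

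The sign of the difference depends on the other patients.

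**The case against.** The case for leaving the text alone has several parts.

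- **Counting every death is legitimate, and the protocol defines PFS with death from any cause.** True, but that choice goes with counting progression after new therapy as well. The SAP discards it.
- **Imaging stops at new therapy (Protocol 8.1.1.1), so little late progression will be on file.** This largely stands for the mCRPC arms. A late PD would have to come from an unscheduled scan, clinical progression, or the disease status collected at follow-up (SAP 8.7.5). With no later assessment on file, the SAP result coincides with ignoring new therapy. The patient who dies is still carried as event-free through an interval with no scheduled imaging.
- **SAP 8.1 cites an FDA guidance.** Its rules are not in the documents, and the explicit derivation in 8.7.4.1 contains no censoring of deaths after new therapy.
- **Few patients qualify.** PCWG3 progression in SAP 8.2 is the earliest of soft-tissue, bone, confirmed PSA or clinical progression, and Arm 1B patients who switch after counted progression already have their main PFS event. This limits the number but does not make it zero. For DoR by iRECIST only iCPD counts, so a responder with unconfirmed progression who starts new therapy may have no counted progression.
- **The endpoints are exploratory**, and planned listings show PFS and further antineoplastic therapies by patient. This stands and sets the severity.

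A reader might infer that PFS and DoR are inflated, and try to size the inflation. The documents do not support that. Against censoring at new therapy, the sign can go either way, as shown above. The gap between 10.84 and 5.55 months belongs to one invented record and is measured against a rule not recommended here as the main analysis. The median OS of 16 to 34 months in Protocol 2.1.1 describes mCRPC generally, not survival after new therapy in this population. Follow-up runs from the last IMP dose (Protocol 8.1.2), not from the start of new therapy.

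**Conclusion.** The inconsistency is real on the explicit wording of SAP 8.7.4.1 and 8.7.4.2. For a patient who starts new therapy without counted progression, PFS, DoR and PFS2 are censored at the last eligible assessment if he is alive, but run to death if he dies before trial discontinuation. As a rule this is neither censoring at new therapy nor ignoring it.

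The direction and size of the effect on Kaplan-Meier estimates and on the exploratory hazard ratios cannot be determined: the documents do not give the number who start new therapy before counted progression, or how many of them die in the trial. The day counts above show how the rule works and are assumptions, not estimates of bias. The primary ORR test is not affected and the endpoints concerned are exploratory. Severity is minor.

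**What to change.** In SAP 8.7.4.1 and 8.7.4.2, apply one rule to both components. When no progression is counted by the start of the first subsequent anti-cancer therapy, keeping the 14-day allowance for PD, censor PFS, DoR and PFS2 at the last evaluable assessment on or before that start. Do not count deaths after that start as events. The existing rules for patients with no post-baseline assessment can stay.

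Report by arm the number of patients whose status changes under this rule. Optionally add a sensitivity analysis that counts both PD and death regardless of new therapy; it will be limited because scheduled mCRPC imaging stops at that point.

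The cost is a sentence in each derivation and one program condition. Start dates of later anti-cancer therapy are already recorded to month 12 (Protocol 1.3 to 1.5), and SAP 8.2 already has rules for imputing missing ones. The downside is that a few deaths become censored, and that censoring may be informative because patients who move to other treatment may differ in prognosis. This is why the counts by arm should be shown.

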### 8.1.2. Survival Status and Biochemical Recurrence

Survival status will be assessed at month 6 and month 12 ( $\pm$ 14 days), beginning from the day of last IMP dose and continues until the patient dies or withdraws from the trial. Patients may be contacted by telephone, E-Mail, or visit. Survival status may be requested more frequently around the time of a database lock. Patients or whose designated family members are not available for this assessment should be entered as "lost to follow-up".

Biochemical recurrence after radical prostatectomy based on post-treatment PSA levels at month 12 will be assessed for patients in Part 2 Arms 2 and 3.

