# 8.4.1. Time Period and Frequency for Collecting AE and SAE Information

All AEs will be collected from signing of the ICF until the safety FU visit at the time points specified in the SoA (Section 1.3 [Part 1 and Part 2 Arms 1A and 1B], Section 1.4 [Part 2 Arms 2 and 3], and Section 1.5 [Part 2 Arm 1B, switch-over patients]).

All SAEs will be collected from signing of the ICF until the safety FU visit at the time points specified in the SoA (Section 1.3 [Part 1 and Part 2 Arms 1A and 1B], Section 1.4 [Part 2 Arms 2 and 3], and Section 1.5 [Part 2 Arm 1B, switch-over patients]).

All SAEs will be recorded and reported to the sponsor or designee immediately and under no circumstance should this exceed 24 h, as indicated in Section 10.3.4. The investigator will submit any updated SAE data to the sponsor within 24 h of it being available.

Investigators are not obligated to actively seek AE or SAE after conclusion of the trial participation. However, if the investigator learns of any SAE, including a death, at any time after a patient has been discharged from the trial, and he/she considers the event to be reasonably related to the trial treatment or trial participation, the investigator must promptly notify the sponsor.

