# 8.4.3. Follow-up of AEs and SAEs

After the initial AE/SAE report, the investigator is required to proactively follow each patient at subsequent visits/contacts. All AEs/SAEs will be followed until resolution, stabilization, the event is otherwise explained, or the patient is lost to follow-up (as defined in Section 7.3). Further information on follow-up procedures is provided in Section 10.3.3.

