#### Overall Survival

OS is defined as the time from the date of first dose of IMP/randomization to the date of death from any cause. OS will be analyzed using the Kaplan-Meier method. Patients alive or patients lost to follow-up at the date of analysis cut-off will be censored at the day of their last date known to be alive. Additional censoring rules will be defined in the SAP.

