# Outcome

The investigator has to assess the outcome of an AE (and not the patient's outcome) at the time of documentation based on the following criteria:

- Recovered/resolved\* (= complete resolution of the AE)
- Recovering/resolving (= AEs which are improving but not yet resolved completely, e.g., decrease in an intensity grade)
- Not recovered/not resolved (= AEs which are ongoing without improving or still present when the patient deceases due to another cause)

CONFIDENTIAL Page 101 of 122

- Recovered/resolved with sequelae\* (= patient recuperated but retained pathological conditions resulting from the AE; the sequelae should be indicated)
- Fatal\*\* (= death due to the AE)
- Unknown (e.g., in case the patient is lost to follow-up)

If the patient has developed permanent or chronic symptoms or if the event requires long-term medication(s), the AE is defined as recovered/resolved with sequelae as soon as no changes of symptoms and/or medication(s) are expected anymore.

An AE that is documented as a worsening of a medical condition already known at baseline, is defined as recovered as soon as the medical condition has returned to baseline status.

\*\* In case of a fatal event, the event term should not be "death" but the underlying event which led to death (death = outcome). If there is more than one AE in a fatal case, only the AE leading to death will be attributed with the outcome "fatal". All other AEs ongoing at the time of death will be attributed with the outcome "not recovered/not resolved". A copy of an autopsy report should be submitted if available.

All ongoing AEs will be followed until resolution, considered by the investigator to be stable or chronic (resolved with sequelae), new systemic anti-cancer treatment (outside the protocol) is initiated, the patient is lost to follow-up or the patient withdraws consent. If no final status is reached at Safety FU-D30 (for all Part 1 patients and Part 2 Arm 1B and Arm 3) or Safety FU-D90 visit (for Part 2 Arm 1A, Arm 1B switch-over patients, and Arm 2), the investigator must confirm the unavailability of a final status.

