Time from treatment start to post treatment prostatectomy for LPC patients (in days):

For date of prostatectomy or radical prostatectomy, missing day will be replaced with the first day of the month. In case month is not reported, missing month will be replaced with July.

Time from treatment start to prostatectomy (days) will be calculated as:

(Date of prostatectomy – date of first IMP administration (W_pro1 or cemiplimab) + 1

Study day:

Study day is defined as follows:

If date of assessment is on or after the date of first IMP administration (W_pro1 or cemiplimab):

- Date of assessment – date of first IMP administration + 1

If date of assessment is before date of first IMP administration (W_pro1 or cemiplimab):

- Date of assessment – date of first IMP administration

Laboratory values with “< xx” or “> xx”:

Any laboratory values given as “< xx” or “> xx” in the database will be imputed with the numeric value of xx without the sign for the descriptive statistics and the calculation of changes from baseline (e.g., a value of < 1 will be imputed as 1 for the calculations).

Last date known to be alive:

Last date known to be alive is defined as last documented date in the database for the patient, including all visit dates, assessment dates (if different from visit dates), trial treatment administration dates, tumor assessment dates, end of treatment dates, date of trial completion or early trial withdrawal date, start/stop dates of AEs, PSA response date, survival follow-up date (where patients survival status is alive), whichever comes last.

Start of Follow-up Period:

Part 1 and Part 2 mCRPC patients: Follow-up period starts at the administration of the last dose of IMP.

Part 2 LPC patients: Follow-up period starts at the last administration of IMP at Cycle 8 or at administration of the last IMP in case of discontinuation of trial treatment.

Pooling of centers:

No pooling of centers is planned for this trial.

Conventions for imputing missing/partially missing dates:

When computations on dates are to be performed, incomplete/missing dates will be imputed using the following rules.

- Missing day, month/year present: If the month/year is the same as the month/year of the first IMP administration date, then impute missing start dates with first IMP administration date. Otherwise, for dates corresponding to a start date, impute with the first day of the month and, for dates corresponding to a stop date, impute with the last day of the month.

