OS is defined as the time from the date of the first dose of IMP to the date of death from any cause. OS will be analyzed using the Kaplan-Meier method. Kaplan-Meier plots will be generated.

In case date of death is reported after trial discontinuation date, this data will not be considered in the OS and the patient will be censored at the day of their last date known to be alive.

Patients alive or patients lost to follow-up at the date of analysis cut-off will be censored at the day of their last date known to be alive.

OS expressed in months = (Date of death from any cause – date of first dose of IMP + 1) / 30.4375 for patients with available death date

or

(Last date of known to be alive – date of first dose of IMP + 1) / 30.4375 in case of censoring.

In the case that date of the first dose of IMP is missing, randomization date will be used for the calculation of OS.

8.7.4.2 Exploratory efficacy endpoints for patients in Arm 1B who are treated with cemiplimab monotherapy following progression on W_pro1

Patients in Arm 1B will be given the option to be treated with cemiplimab monotherapy following progression on W_pro1 monotherapy treatment and will be assessed for some exploratory efficacy endpoints, where the last measurement prior to start of cemiplimab treatment will serve as baseline measurement and the time-to-event endpoints (DoR, and PFS) will start from first dose of cemiplimab treatment. In particular, the last radiographic tumor assessment prior to cemiplimab treatment will re-define target and non-target lesions as basis for tumor response assessment on cemiplimab treatment. Additionally, PFS2 will be evaluated based on initial start of IMP.

These exploratory efficacy analyses will be performed using the subsequent cemiplimab monotherapy on progression set.

Objective Response Rate based on PCWG3 and iRECIST (central reading)

ORR will be analyzed separately for PCWG3 and iRECIST (central reading).

The ORR is defined as the number of patients with CR or PR as best objective response per PCWG3 (or number of patients with iCR or iPR as best objective response per iRECIST (central reading)) after start of cemiplimab treatment, divided by the number of patients in the subsequent cemiplimab monotherapy on progression set.

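### The SAP's overall survival rule ignores deaths after trial discontinuation but still counts alive time after it, so any bias in this exploratory endpoint is upward, though probably small

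*SAP*

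**What the plan says.** **Deaths.** SAP 8.7.4.1 (Overall survival): "In case date of death is reported after trial discontinuation date, this data will not be considered in the OS". Such a patient is censored at the last date known to be alive, not at the discontinuation date. The event formula in the same section applies "for patients with available death date" and does not repeat the restriction.

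**Alive dates.** SAP 8.2 takes the latest of many database dates, including "start/stop dates of AEs, PSA response date, survival follow-up date" (the last where the patient was alive). The trial completion or early withdrawal date is one item on that list. It therefore acts as a floor, not a ceiling.

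**Source of the rule.** The Overall Survival paragraph in Protocol 9.4.4 does not exclude later deaths, but adds: "Additional censoring rules will be defined in the SAP".

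**What is collected after leaving.** Under Protocol 8.1.2, survival follow-up "continues until the patient dies or withdraws from the trial". Protocol 8.4.3 is wider for adverse events: "All AEs/SAEs will be followed until resolution, stabilization, the event is otherwise explained, or the patient is lost to follow-up". Protocol 10.3.3 (Outcome) narrows this, stopping for example when "the patient is lost to follow-up or the patient withdraws consent". Protocol 8.4.1 covers the case "if the investigator learns of any SAE, including a death, at any time after a patient has been discharged from the trial", but requires notification only if the investigator considers the event reasonably related to treatment or participation.

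**The concern.** A censoring rule should treat death and survival alike after the point at which follow-up stops counting. Here it does not. A patient with an alive record after leaving the trial stays in the risk set past discontinuation. The same patient's death in that period is discarded. Those patients enlarge the denominator of the hazard and can never enter the numerator.

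At stake are the Kaplan-Meier OS estimates for all arms and the exploratory log-rank tests and hazard ratios in SAP 8.1. The effect could differ between arms if later records are more frequent in one of them. The only formal hypothesis concerns objective response rate and is untouched.

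**Working it through.** The documents state no OS event count, discontinuation rate or share of patients with later dates, so there is no plan figure to reproduce.

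**1. Direction.** At any time t, let R_on be the patients at risk who are still in the trial, and R_off those kept at risk only by an alive date after discontinuation. Deaths count only in R_on. If leaving is unrelated to prognosis,

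estimated hazard = true hazard × R_on / (R_on + R_off).

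The ratio is 1 when R_off = 0 and below 1 otherwise. Estimated OS is therefore correct or too high, never too low. If alive dates are capped at discontinuation, R_off = 0 and the estimate is correct under the same condition.

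**2. Is R_off > 0 possible?** Yes, mainly through adverse event stop dates after leaving. A survival contact recorded after leaving would also count, but none is planned once a patient withdraws.

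**3. Size (illustration).** Inputs:
- Median OS of 16 or 34 months, the range in Protocol 2.1.1, with exponential survival. True 12-month OS is 0.5^(12/16) = 59.5% and 0.5^(12/34) = 78.3%.
- Assumed: time to leaving is exponential with median 12 or 24 months and unrelated to prognosis; data cut-off is uniform over 12 to 30 months.
- Assumed: a share f of off-trial patients has a later alive date. Survivors are known alive at cut-off. For those who died, the last alive date is uniform between leaving and death, and the death is ignored.

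Simulated 12-month OS (%), 1,000,000 patients per row:

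| Median OS / leaving (months) | f = 0, same as cap | f = 2% | f = 5% | f = 10% |
|---|---|---|---|---|
| 16 / 12 | 59.46 | 59.68 | 60.02 | 60.54 |
| 16 / 24 | 59.52 | 59.62 | 59.76 | 60.01 |
| 34 / 12 | 78.33 | 78.48 | 78.71 | 79.07 |
| 34 / 24 | 78.31 | 78.38 | 78.48 | 78.64 |

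The rise is 0.1 to 0.2 points at f = 2% and 0.3 to 1.1 points at f = 10%.

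**4. Adverse event route only.** With a stop date within three months of leaving in 10% of off-trial patients, the four rows give 59.72, 59.64, 78.49 and 78.39, a rise of 0.1 to 0.3 points. With 2% affected, the rise is under 0.1 point.

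**5. Against sampling error.** For a 12-month rate of 59.5%, ignoring censoring, 1.96 × √(0.595 × 0.405 / n) is 16.7 points at n = 33 and 21.5 points at n = 20.

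**6. What a cap cannot do.** With median OS 16 and leaving median 12, suppose mortality doubles after leaving. True 12-month OS is then 52.3%, but the capped estimate is 59.5%. The cap removes the asymmetry, not bias from leaving that is linked to prognosis.

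**The case against.** **The dates should hardly exist.** Survival contact stops at withdrawal, and Protocol 7.2 expects withdrawal to be uncommon, whereas the illustration puts roughly 31% to 58% of patients off trial before death or cut-off. Protocol 10.3.3 stops adverse event follow-up at consent withdrawal, and at the Day 30 or Day 90 safety visit the investigator confirms if no final status is available. Deaths after discharge need be reported only if judged related. All of this stands. It makes the larger table entries unlikely and leaves adverse event stop dates as the main documented route. It does not remove the asymmetry.

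**The SAP may set censoring rules.** It may, and dropping later deaths is not biased in itself if alive time stops at the same date and leaving is unrelated to prognosis. The fault is the mismatch.

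**Stronger readings a reader might infer:**
- *The event formula contradicts the exclusion.* The sentence that orders censoring settles it; the formula is only loosely worded.
- *Arm 1B deaths after the switch to cemiplimab are removed from OS.* SAP 8.1 excludes post-switch efficacy data and omits OS from its list of exceptions. But that list is tied to the last tumor assessment before cemiplimab. SAP 8.7.4 names OS for switchers, SAP 8.7.4.2 derives it as in 8.7.4.1, and 8.7.4.1 has no censoring at the switch. What remains is a missing word in a list.
- *The OS clock for switchers is wrong or unclear.* Protocol 1.1 and 3 and SAP 3.1 and 8.7.4.2 all start it at the first trial treatment. Time before the switch is event-free by selection, so the figure does not describe survival from cemiplimab, but the definition is consistent and is not an error.

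**Conclusion.** The asymmetry is in the text: later deaths are ignored while later alive time counts. Given leaving unrelated to prognosis, any resulting bias in OS is upward. It is nil if no alive dates follow discontinuation, and probably at most a few tenths of a point at 12 months if only some adverse event stop dates do. Figures near 1 point need survival contact after leaving, which the protocol does not plan. All sizes rest on assumed shares, exponential survival and leaving unrelated to prognosis.

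The documents do not support a claim that OS will be materially inflated, that Arm 1B loses its post-switch deaths, or that the switchers' OS clock is mistaken. OS is exploratory. This is an inexpensive correction to make before analysis, not a threat to the trial's conclusions.

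**What to change.** 1. In SAP 8.2 or 8.7.4.1, state that for OS the last date known to be alive is capped at the trial discontinuation date for every patient, whether or not a later death is known. Use the date that governs the death rule, which is leaving the trial, not ending a treatment.
2. Word the event branch of the OS formula as deaths on or before that date.
3. State that the cap does not remove bias if leaving is linked to prognosis.
4. In SAP 8.1, add OS to the permitted uses of Arm 1B post-switch data, in line with 8.7.4 and 8.7.4.2, and say that post-switch deaths and alive dates stay in the main Arm 1B OS analysis.

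The cost is SAP wording and a one-line derivation change on data already collected, with no protocol change. The downside is that some known follow-up is discarded.

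Optional only: OS from the first cemiplimab dose for switchers, beside the protocol-defined figure (one table, one figure).

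Separately, Protocol 1.3 counts the 28-day switch window from confirmation of progression and Protocol 1.5 counts it from progression. These passages must be reconciled; the OS rule does not depend on it.
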